5.4 Laboratory Assessments

Normal ranges for the study laboratory parameters must be supplied to Roche before the study starts.

Efficacy Laboratory Assessments

Laboratory parameters will not be considered for the purpose of efficacy assessment.

Safety Laboratory Assessments

All safety laboratory assessments will be performed at local laboratories.

The following will be completed according to the Schedule of Assessments:

Blood tests with counts of the three series (leukocytes with neutrophils, haemoglobin, and platelets). This information will be obtained in the 21 days before initiation of treatment.

Biochemistry: LDH, alkaline phosphatase, ASAT, ALAT, total bilirubin, serum creatinine, creatinine clearance (if indicated), calcium, electrolytes, glucose and urea. This information will be obtained in the 21 days before initiation of treatment.

Prothrombin time, INR and aPTT. This information will be obtained in the 7 days before initiation of treatment.

Pregnancy test (urine or blood) in women of childbearing age, to be performed at screening and in the 1st day of study treatment (baseline), before the intake of study medication and at the end of study treatment.

5.5 Safety Follow-Up Visit (28 days after last study drug administration)

Patients who discontinued therapy due to disease progression, unacceptable toxicity or patient's decision, should have a safety follow-up completed 28 days after last dose of study treatment. This assessment should include physical examination, ECOG performance status, haematology, biochemistry, concomitant medications, adverse events and subsequent therapy for NSCLC.

5.6 Survival Follow-up Phase

After the final visit has been completed the patient should be followed every 6 months (\pm 15 days), or as appropriate evaluated by the investigator, for collection of subsequent therapies and survival status.

6. INVESTIGATIONAL MEDICINAL PRODUCT

6.1 Dose and Schedule of IMP and Comparator(S)

Erlotinib will be administered as single daily oral dose of 150 mg, until disease progression or unacceptable toxicity. No dose escalation of erlotinib is permitted. Dose reduction will be allowed according to protocol (Section 6.1.).

Dose Modifications, Interruptions and Delays

Reduction of dosing for adverse events may take place at any time during the study.

Diarrhoea and skin rash are the major side effects associated with erlotinib. Other known side effects, include dry skin, fatigue, pruritus, nausea, vomiting, anorexia, abdominal pain,

gastrointestinal perforation, dry mouth, dry eye, and headache. Dose reductions can be made according to the system exhibiting the greatest degree of toxicity. All toxicities will be graded according to the NCI CTC-AE version 4.0.

In the event of toxicity (e.g., diarrhoea, rash) that is not controlled by optimal supportive care, or not tolerated due to any reason, regardless of severity, the daily dose of erlotinib will be decreased to 100 mg/day.

Within 2 weeks following a dose reduction, erlotinib related toxicity must improve by at least one NCI-CTC grade and be NCI-CTC Grade 2 or better (any ocular toxicity must improve to NCI-CTC Grade 1), or a further dose reduction to 50 mg/day will be required.

Table 3 - Dose Level Reductions

Starting Dose	First reduction	Second reduction
150 mg/day	100 mg/day	50 mg/day

Patients who cannot tolerate a dose reduction to 50 mg/day will be permanently discontinued from the study.

Dosing may be interrupted for a maximum of 2 weeks if clinically indicated and if the toxicity is not controlled by optimal supportive medication.

Once a patient has had a dose reduction for toxicity, the dose will not be re-escalated except in the case of erlotinib related rash. In the event of a rash, dose can be re-escalated when rash is NCI-CTC Grade 2.

Supportive Care Guidelines

Diarrhoea:

Diarrhoea has been commonly observed (~ 50% patients) and is usually transient in nature. Previous trials have shown that the frequency and severity of diarrhoea rarely hindered administration of erlotinib and could be managed with loperamide. The recommended dose is loperamide 4 mg at first onset, followed by 2 mg every 2 – 4 hours until diarrhoea-free for 12 hours. Patients with diarrhoea should have regular monitoring of their electrolytes and be adequately rehydrated (see table 2 below). Prophylactic use of anti-diarrhoea treatments is not advised.

Table 4 - Guidelines for management of erlotinib-related toxic effects:

Toxicity	Grade	Guideline for management	Dose modification of erlotinib*
Keratitis	2	Interrupt the treatment. Ophthalmologic assessment.	Hold until recovery, and then restart at reduced dose. Continue regular ophthalmological assessments while on treatment.
	≥ 3	Discontinue treatment and seek ophthalmological advice	
Diarrhoea	1	Consider Loperamide (4 mg at first onset, followed by 2 mg every 2 – 4 hours until diarrhoea free for 12 hours) and appropriate rehydration.	None
	2	Loperamide (4 mg at first onset, followed by 2 mg every 2 – 4 hours until diarrhoea free for 12 hours) and appropriate rehydration.	Interrupt
	3	Interrupt and give appropriate rehydration, monitor electrolyte balance and renal function until resolution to Grade ≤ 1; restart at reduced dose.	Interrupt
	4	Discontinue treatment	
Rash	1	No intervention	None
	2	Any of the following: minocycline ^a , topical tetracycline or clindamycin, topical silver sulfadiazine, diphenhydramine, oral prednisone (short course)	None**
	3		Hold until recovery to ≤ grade 2, and then restart the dose.
	4	Discontinue treatment	
Other toxicity	≥ 2 prolonged clinically significant toxicity	Treatment as appropriate	Hold until recovery to ≤ grade 1, and then restart at reduced dose.

* If no recovery after 14 days of holding drug, patients should be discontinued from the study

** If dose has been previously held for grade 2 rash or diarrhoea, and grade 2 symptoms recur, or if the patient finds the symptoms unacceptable, hold dose until recovery to ≤ grade 1 and then reduce the dose.

^a Recommended dose: 200 mg p.o. b.i.d. (loading dose), followed by 100 mg p.o. b.i.d. for 7-10 days.

Rash:

Skin rash or dermatosis (Grade 1 – 2) has been observed during the first several days of treatment with erlotinib in more than 50% and has been observed to diminish in severity despite continued treatment in many patients. In some patients, particularly when a superimposed infection is suspected, this rash appeared to improve with topical and oral antibiotics. In general, rash manifests as a mild or moderate erythematous and papulopustular rash, which may occur, or worsen, in sun exposed areas. For patients who are exposed to sun, protective clothing, and/or use of sun screen (e.g. mineral-containing) may be advisable. In patients with severe rash, treatment may need to be discontinued or the dose reduced (see table 4 below).

In the event of a rash, dose can be re-escalated when rash is \leq grade 2. Within 2 weeks following a dose reduction, erlotinib related toxicity must improve by at least one NCI-CTC grade and be NCI-CTC Grade 2, or further dose reduction by one level will be required. Dosing may be interrupted for a maximum of 2 weeks if clinically indicated and if the toxicity is not controlled by optimal supportive medication. Once a patient has had a dose reduction for toxicity, the dose will not be re-escalated except in the case of erlotinib related rash.

Stevens-Johnson syndrome

Very rare cases suggestive of Stevens-Johnson syndrome/Toxic epidermal necrolysis have been reported, which in some cases were fatal - see section 4.8 of SPC (30). Erlotinib treatment should be interrupted or discontinued if the patient develops severe bullous, blistering or exfoliating conditions.

Interstitial Lung Disease (ILD)

In patients who develop acute onset of new and/or progressive unexplained pulmonary symptoms such as dyspnoea, cough and fever, erlotinib therapy should be interrupted pending diagnostic evaluation. If ILD is diagnosed, Erlotinib should be discontinued and appropriate treatment initiated as necessary - see section 4.8 of the SPC (30). If ILD is excluded, re-medication is considered at the same dose.

Missed doses:

Doses should be taken at the same time each day. If the patient vomits after ingesting the tablets, the dose will be replaced only if the tablets can actually be seen and counted. A missed dose normally taken in the morning can be taken any time during the same day. Patients will be asked to report any missed doses to study site personnel.

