3. STUDY DESIGN

3.1 Overview of Study Design

This is a local open-label, multi-centre Phase II study of the anti-tumoral activity of erlotinib (Tarceva[®]; 150 mg) evaluated by objective response rate (ORR) in patients with NSCLC in locally advanced or metastatic stages who have not received previous chemotherapy for their disease and who present activating mutations in the TK domain of the EGFR.

Summary of the study design is shown in Figure 1.

Figure 1 - Summary of study design

Rationale for Study Design

In this trial erlotinib is given in first-line treatment for advanced NSCLC.

Although this trial is non-randomized phase II trial, as Erlotinib is currently used in clinical practice to treat NSCLC it closely reflects clinical practice.

Any patient with locally advanced or metastatic non-small cell lung cancer disease found to have an EGFR Exon 19 deletion or exon 21 substitution L858R in the TK domain of EGFR gene will be offered first-line treatment with erlotinib.

The primary efficacy variable will be ORR.

Rationale for Dose Selection

The recommended daily dose of erlotinib was established at 150 mg, to be continued daily until disease progression.

All enrolled patients will receive recommended dose of erlotinib (150 mg/day). No dose escalation is permitted. Erlotinib dose will be reduced for toxicities as detailed in Section 6.1. Patients will be treated until progression of disease or unacceptable toxicity.

End of Study

This study is event-driven, with a recruitment period that will last until the end of March 2012 or until the number of patients aimed for the protocol (30) is achieved, whatever occurs first. Patients are to be treated until disease progression, unacceptable toxicity or patient request for discontinuation.

The study will end when the last patient has stopped erlotinib therapy and completed their last safety follow-up visit (28 days after last study drug administration). For all patients who have discontinued study drug treatment and are alive, information on survival will be collected.

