4.6.3. Duration of stable disease

Stable disease is measured from the start of the treatment (in randomized trials, from date of randomization) until the criteria for progression are met, taking as reference the smallest sum on study (if the baseline sum is the smallest, this is the reference for calculation of PD). The clinical relevance of the duration of stable disease varies in different studies and diseases. If the proportion of patients achieving stable disease for a minimum period of time is an endpoint of importance in a particular trial, the protocol should specify the minimal time interval required between two measurements for determination of stable disease.

19. Appendix 2: The ECOG Performance Scale

The Eastern Cooperative Oncology Group Performance Status Assessment
(Oken et al., 1982)

Grade	ECOG
0	Fully active, able to carry on all pre-disease performance without restriction.
1	Restricted in physically strenuous activity but ambulatory and able to carry out work of a light or sedentary nature, e.g., light house work, office work.
2	Ambulatory and capable of all self-care but unable to carry out any work activities. Up and about more than 50% of waking hours.
3	Capable of only limited self-care, confined to bed or chair more than 50% of waking hours.
4	Completely disabled. Cannot carry on any self-care. Totally confined to bed or chair.
5	Dead.

20. Appendix 3: Information on Potential Interactions

Erlotinib is metabolized in the liver by the hepatic cytochromes in humans, primarily CYP3A4 and to a lesser extent by CYP1A2, and the pulmonary isoform CYP1A1. Potential interactions may occur with drugs which are metabolized by, or are inhibitors or inducers of, these enzymes.

Potent inhibitors of CYP3A4 activity decrease erlotinib metabolism and increase erlotinib plasma concentrations. Inhibition of CYP3A4 metabolism by ketoconazole (200 mg p.o. BID for 5 days) resulted in increased exposure to erlotinib (86% in median erlotinib exposure (AUC)) and a 69% increase in C_{max} when compared to erlotinib alone. When erlotinib was co-administered with ciprofloxacin, an inhibitor of both CYP3A4 and CYP1A2, the erlotinib exposure (AUC) and maximum concentration (C_{max}) increased by 39% and 17%, respectively. Therefore caution should be used when administering erlotinib with potent CYP3A4 or combined CYP3A4/CYP1A2 inhibitors. In these situations, the dose of erlotinib should be reduced if toxicity is observed.

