Potent inducers of CYP3A4 activity increase erlotinib metabolism and significantly decrease erlotinib plasma concentrations. Induction of CYP3A4 metabolism by rifampicin (600 mg p.o. QD for 7 days) resulted in a 69% decrease in the median erlotinib AUC, following a 150 mg dose of erlotinib as compared to erlotinib alone.

Pre-treatment and co-administration of rifampicin with a single 450 mg dose of erlotinib resulted in a mean erlotinib exposure (AUC) of 57.5% of that after a single 150 mg erlotinib dose in the absence of rifampicin treatment. Alternative treatments lacking potent CYP3A4 inducing activity should be considered when possible. For patients who require concomitant treatment with erlotinib and a potent CYP3A4 inducer such as rifampicin an increase in dose to 300 mg should be considered while their safety is closely monitored, and if well tolerated for more than 2 weeks, further increase to 450 mg could be considered with close safety monitoring. Higher doses have not been studied in this setting.

Pre-treatment or co-administration of erlotinib did not alter the clearance of the prototypical CYP3A4 substrates midazolam and erythromycin. Significant interactions with the clearance of other CYP3A4 substrates are therefore unlikely. Oral availability of midazolam did appear to decrease by up to 24%, which was however not attributed to effects on CYP3A4 activity.

The solubility of erlotinib is pH dependent. Erlotinib solubility decreases as pH increases. Drugs that alter the pH of the upper GI tract may alter the solubility of erlotinib and hence its bioavailability. Co-administration of erlotinib with omeprazole, a proton pump inhibitor, decreased the erlotinib exposure (AUC) and C_{max} by 46% and 61%, respectively. There was no change to T_{max} or half-life. Concomitant administration of erlotinib with 300 mg ranitidine, an H_2 -receptor antagonist, decreased erlotinib exposure (AUC) and C_{max} by 33% and 54%, respectively. Therefore, co-administration of drugs reducing gastric acid production with erlotinib should be avoided where possible. Increasing the dose of erlotinib when co-administered with such agents is not likely to compensate for this loss of exposure. However when erlotinib was dosed in a staggered manner, 2 hours before or 10 hours after ranitidine 150 mg b.i.d., erlotinib exposure (AUC) and C_{max} decreased only by 15% and 17%, respectively. If patients need to be treated with such drugs, then an H_2 -receptor

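### Protocol Sections 3.1 and 6.1 rule out any dose above 150 mg/day, yet Appendix 3 raises 300 mg and then 450 mg for patients who need a potent CYP3A4 inducer, and nothing says which text governs

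*Protocol*

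**What the plan says.** **Dosing sections.** Protocol Section 3.1, under the rationale for dose selection, sets 150 mg/day for everyone enrolled and adds "No dose escalation is permitted". Section 6.1 repeats it: "No dose escalation of erlotinib is permitted". Section 6.1 then sets out reductions to 100 and 50 mg/day and one exception on the way up: after a toxicity reduction, "the dose will not be re-escalated except in the case of erlotinib related rash". It does not mention CYP3A4 inducers.

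**Interaction text.** The appendix headed "Appendix 3: Information on Potential Interactions" deals with potent inducers such as rifampicin. It puts avoidance first: "Alternative treatments lacking potent CYP3A4 inducing activity should be considered when possible". For patients who must take one, it says that "an increase in dose to 300 mg should be considered while their safety is closely monitored, and if well tolerated for more than 2 weeks", a further rise to 450 mg is open to consideration under close safety monitoring.

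**Related text.** Section 4.5 asks for caution with CYP3A4 inhibitors and inducers. Inducers are neither on its list of treatments not permitted nor among the exclusion criteria in Section 4.3. Section 7.3 warns of drug-drug interactions and refers to Appendix 4, which is the AJCC staging chapter. Protocol Table 6 and SAP 5.2.2 class deviations in study-drug dosing as Major, and a Major violation removes the patient from the per-protocol population.

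**The concern.** A site with a patient who needs a potent inducer finds a flat prohibition in two places and, in a third, advice to consider twice and then three times the trial dose. If it looks for guidance through Section 7.3, it is sent to the wrong appendix.

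Two things are at stake. The first is conduct: two sites could dose the same kind of patient differently, and each could cite the protocol. The second is classification: the same dosing is a Major deviation if Section 6.1 governs, and is not one if Appendix 3 is an exception. That leaves per-protocol membership to be settled after the event, in an open-label study where the outcome may already be known.

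**Working it through.** The documents give no figure to reproduce on this point. The check is a comparison of texts followed by short arithmetic.

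**1. Are the Appendix 3 doses escalations?** 300/150 = 2.0 and 450/150 = 3.0. Both are increases from the starting dose, not a return to it after a reduction, so the rash exception does not cover them.

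**2. Can the case arise?** Yes. Inducers are neither excluded (Section 4.3) nor prohibited (Section 4.5), so taking one is not in itself a prohibited-medication deviation under Table 6.

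**3. Does any passage set precedence?** None was found in Protocol Sections 3.1, 4.5, 6.1, 7.3, 8.2.3 or Appendix 3, or in the SAP.

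**4. What follows from each reading?**
- *Section 6.1 governs:* dosing at 300 or 450 mg is a Major deviation and the patient leaves the per-protocol set. The SAP dose derivations need no change on this account.
- *Appendix 3 is an exception:* the dosing is within protocol and the patient stays. The SAP derivations then have a gap (step 6).

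**5. Size for the response rate.** Assume all 30 patients are otherwise in the per-protocol set, with r responders.
- Remove one non-responder: r/29 − r/30 = r/870.
- Remove one responder: (r − 1)/29 − r/30 = −(30 − r)/870.
- Largest absolute change: 29/870 = 3.3 points.
- At the response rates the protocol cites for first-line erlotinib, 70.6% and 82.9% (r about 21 and 25 of 30), removing a responder changes the rate by −9/870 = −1.0 or −5/870 = −0.6 points. Removing a non-responder changes it by +21/870 = +2.4 or +25/870 = +2.9 points.
- The documents give no frequency of inducer use. For k patients removed, the bound is k/30: 6.7 points for two, 10.0 for three.
- The planned margin of error is about ±17.5 points.
- The ITT population is everyone enrolled to the treatment phase, so its membership does not change.

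**6. SAP derivations, only if doses above 150 mg are allowed.** The SAP Appendix 3 average-dose formula has terms for 150, 100 and 50 mg only. For an assumed 28 days at 150 mg and 28 days at 300 mg it gives (150 × 28)/56 = 75 mg/day, against an actual (150 × 28 + 300 × 28)/56 = 225 mg/day. The compliance ratio divides tablets used by days, adjusted only for 50 mg. With 150 mg tablets and full adherence it would read 200% at 300 mg and 300% at 450 mg.

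**7. A separate minor point, whichever text governs.** Section 6.1 says "Dosing may be interrupted for a maximum of 2 weeks if clinically indicated", but the compliance denominator counts every day between visits. With one tablet a day, a 14-day hold in a 56-day interval and every other dose taken, the ratio is 42/56 = 75%, against the 80% threshold in SAP 5.3.10.1. This is a single-interval figure. With a second, fully dosed interval the patient stands at (42 + 56)/112 = 87.5%, and averaging the two interval ratios gives the same.

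**The case against.** The best defence is that there is no true conflict. Sections 3.1 and 6.1 are the dosing rule: categorical, stated twice, with their own exception. Appendix 3 is headed as information, puts alternatives first and only asks that higher doses be considered. Nothing in Section 6 sends a site there for dosing. On that reading Section 6.1 governs, Table 6 already answers the per-protocol question, and the Section 7.3 pointer is a typing error that the table of contents lets a reader correct.

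Much of this is fair, and it is a reasonable guess at what was intended. It does not close the matter, because Appendix 3 is not pure background. It restates a trial rule (coumarin use excludes a patient) and gives a mandatory instruction on timing erlotinib around H2-receptor antagonists. A site cannot tell which of its sentences bind.

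Some stronger readings should be resisted:
- A reader might infer that the SAP expects escalation, because Table 28 has a category for an increased dose. Re-escalation after rash explains that category equally well.
- A reader might call the average-dose formula wrong. It agrees with Sections 3.1 and 6.1, and is a defect only if higher doses are allowed.
- A reader might infer lost or excess exposure at 300 mg. Appendix 3 gives no exposure figure for 300 mg with an inducer.
- A reader might treat the compliance point as a threat to efficacy. The 80% flag is a descriptive row in SAP Table 22 and is not part of the per-protocol definition. Whether held days should count is partly a matter of choice.

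**Conclusion.** The protocol contradicts itself on dosing for patients who need a potent CYP3A4 inducer. This rests on the text alone, and confidence in it is high. It should be fixed because sites hold conflicting instructions on a two- to three-fold dose difference, not because the statistics are at risk.

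The 3.3-point bound for one patient assumes that nobody else has been excluded from a per-protocol set of 30. With n patients in the set the bound is 1/n, so a smaller set raises it. The number of patients affected cannot be judged from the documents. A reader might infer that the primary result is compromised; the documents do not support that, since the ITT analysis is primary and its membership does not depend on how the dosing is classified.

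This review takes no view on which dosing text is right.

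**What to change.** 1. Reconcile Protocol Sections 3.1, 4.5 and 6.1 with Appendix 3 so that there is one instruction for patients who need a potent CYP3A4 inducer. The sponsor's clinical team decides its content.
2. Correct the Section 7.3 reference from Appendix 4 to Appendix 3.
3. Only if the reconciled text allows doses above 150 mg: state in Protocol Table 6 and SAP 5.2.2 how such dosing is classified, and extend the SAP average-dose formula and compliance denominator to the doses prescribed.
4. Separately, and of minor weight: consider using tablets prescribed, with none on held days, as the compliance denominator.

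The cost is one protocol clarification and one cross-reference, submitted to the ethics committee as Section 12 requires, and one SAP definition if item 4 is taken up. Item 3 costs nothing unless it is triggered. No patients, visits or procedures are added.

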7.3 Warnings and Precautions

Interstitial Lung Disease (ILD)-Like Events

Cases of interstitial lung disease (ILD)-like events, including fatalities, have been reported uncommonly in patients receiving erlotinib for treatment of NSCLC, pancreatic cancer or other advanced solid tumours. In pivotal study BR 21, in NSCLC, the incidence of serious ILD-like events was 0.8% in each of the placebo and erlotinib arms. In the pancreatic cancer study in combination with gemcitabine, the incidence of ILD-like events was 2.5% in the erlotinib plus gemcitabine group versus 0.4% in the placebo plus gemcitabine treated group. The overall incidence in patients treated with erlotinib from all studies (including uncontrolled studies and studies with concurrent chemotherapy) is approximately 0.6%. Some examples of reported diagnoses in patients suspected of having ILD-like events include pneumonitis, radiation pneumonitis, hypersensitivity pneumonitis, interstitial pneumonia, interstitial lung disease, obliterative bronchiolitis, pulmonary fibrosis, acute respiratory distress syndrome, lung infiltration and alveolitis. These ILD-like events started from a few days to several months after initiating erlotinib therapy. Most of the cases were associated with confounding or contributing factors such as concomitant or prior chemotherapy, prior radiotherapy, pre-existing parenchymal lung disease, metastatic lung disease, or pulmonary infections.

In patients who develop acute onset of new and/or progressive unexplained pulmonary symptoms, such as dyspnoea, cough and fever, erlotinib therapy should be interrupted pending diagnostic evaluation. If ILD is diagnosed, erlotinib should be discontinued and appropriate treatment initiated as necessary.

Diarrhoea, Dehydration, Electrolyte Imbalance and Renal Failure

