Diarrhoea has occurred in patients on erlotinib, and moderate or severe diarrhoea should be treated with loperamide. In some cases, dose reduction may be necessary. In the event of severe or persistent diarrhoea, nausea, anorexia, or vomiting associated with dehydration, erlotinib therapy should be interrupted and appropriate measures should be taken to treat the dehydration. There have been rare reports of hypokalaemia and renal failure (including fatalities). Some reports of renal failure were secondary to severe dehydration due to diarrhoea, vomiting and/or anorexia while others were confounded by concomitant chemotherapy. In more severe or persistent cases of diarrhoea, or cases leading to dehydration, particularly in groups of patients with aggravating risk factors (concomitant medications, symptoms or diseases or other predisposing conditions including advanced age), erlotinib therapy should be interrupted and appropriate measures should be taken to intensively rehydrate the patients intravenously. In addition, renal function and serum electrolytes including potassium should be monitored in patients at risk of dehydration.

Hepatitis, Hepatic Failure

Rare cases of hepatic failure (including fatalities) have been reported during use of erlotinib. Confounding factors have included pre-existing liver disease or concomitant hepatotoxic medications. Therefore, in such patients, periodic liver function testing should be considered. Erlotinib dosing should be interrupted if changes in liver function are severe.

Gastrointestinal perforation

Patients receiving erlotinib are at increased risk of developing gastrointestinal perforation, which was observed uncommonly (including some cases with a fatal outcome). Patients receiving concomitant anti-angiogenic agents, corticosteroids, non-steroidal anti-inflammatory drugs (NSAIDs), and/or taxane based chemotherapy, or who have prior history of peptic ulceration or diverticular disease are at increased risk. Erlotinib should be permanently discontinued in patients who develop gastrointestinal perforation).

Bullous and exfoliative skin disorders

Bullous, blistering and exfoliative skin conditions have been reported, including very rare cases suggestive of Stevens-Johnson syndrome/toxic epidermal necrolysis, which in some cases were fatal. Erlotinib treatment should be interrupted or discontinued if the patient develops severe bullous, blistering or exfoliating conditions.

Ocular Disorders

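### For gastrointestinal perforation, Protocol section 6.1 and Table 4 leave a hold-and-restart route open, while section 7.3 calls for permanent discontinuation

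*Protocol*

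**What the plan says.** Three places in the Protocol bear on dosing after a gastrointestinal perforation.

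- **Section 6.1, Dose Modifications, Interruptions and Delays.** Perforation appears in the list of other known side effects, and the text moves directly to dose reduction: "gastrointestinal perforation, dry mouth, dry eye, and headache. Dose reductions can be made according to the system exhibiting the greatest degree of toxicity". A general rule follows for toxicity that supportive care does not control, or that is "not tolerated due to any reason, regardless of severity, the daily dose of erlotinib will be decreased to 100 mg/day".
- **Section 6.1, Table 4.** The named rows are keratitis, diarrhoea and rash. The remaining row, Other toxicity, is triggered by "≥ 2 prolonged clinically significant toxicity" and its dose action is "Hold until recovery to ≤ grade 1, and then restart at reduced dose". A footnote limits the hold: "If no recovery after 14 days of holding drug, patients should be discontinued from the study".
- **Section 7.3, Gastrointestinal perforation.** "Erlotinib should be permanently discontinued in patients who develop gastrointestinal perforation". The same paragraph calls the event uncommon and notes that some cases were fatal.

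Section 3.1 (Rationale for Dose Selection) sends the reader to section 6.1 for dose reduction on toxicity. It does not mention 7.3.

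**The concern.** Section 6.1 is where the protocol sends a reader for toxicity dosing, and it deals with perforation only by listing it ahead of a dose-reduction rule. An investigator who looks up the event there finds reduction, or hold and restart, and no instruction to stop. An investigator who looks in 7.3 finds a permanent stop. The two routes cannot both be followed once the patient has recovered.

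What is at stake is first patient safety: one part of the protocol leaves room for re-exposure after an event for which another part says drug should not be given again. The second consequence is analytic. Protocol Table 6, repeated in SAP section 5.2.2, treats both a departure from the dose reduction schedule and a failure to stop treatment once a withdrawal criterion is met as major deviations. With the passages unreconciled, the classification of such a patient depends on which passage the person coding the deviation has in mind.

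**Working it through.** The plan states no figure on this point and no calculation applies. The check is a comparison of the passages.

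**Step 1: what each passage directs for perforation.**

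| Place in the Protocol | Names perforation? | Direction |
|---|---|---|
| 6.1, side-effect list and next sentence | Yes | Reduction permitted |
| 6.1, general rule | No, but applies whatever the severity | Reduce to 100 mg/day |
| 6.1, Table 4, Other toxicity | No; reached by default | Hold, then restart at a lower dose |
| 7.3, perforation paragraph | Yes | Permanent discontinuation |

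**Step 2: does Table 4 reach the event?** It has no perforation row. A perforation of grade 2 or higher that is judged prolonged and clinically significant meets the trigger of the Other toxicity row. Prolonged is not defined, and no event is excluded from the row.

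**Step 3: does the 14-day footnote remove the conflict?** Only in part. It stops patients who have not recovered after 14 days of holding. A patient who recovers to grade 1 or better within that time meets the restart condition, and for that patient Table 4 and 7.3 diverge.

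**Step 4: does 6.1 supply the stop elsewhere?** After Table 4 it has separate paragraphs for Stevens-Johnson syndrome and ILD, each in line with 7.3. For ILD, 6.1 reads "If ILD is diagnosed, Erlotinib should be discontinued and appropriate treatment initiated as necessary" and 7.3 reads "If ILD is diagnosed, erlotinib should be discontinued and appropriate treatment initiated as necessary". There is no such paragraph for perforation and no pointer to 7.3 for it. Section 4.6 allows the investigator to withdraw a subject for an adverse event, but does not require a stop after perforation.

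**Step 5: how would Table 6 code the patient?**

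- Drug restarted: compliant if judged against Table 4; a major deviation if the 7.3 instruction counts as a withdrawal criterion.
- Drug stopped for good: compliant with 7.3; open to being read as a departure from the dose reduction schedule if judged against Table 4.

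The documents do not say which reading applies.

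**Step 6: size.** No perforation rate is given, so no expected count can be derived. Each affected patient is 1 of 30, and 1/30 = 3.3% of the planned treated patients. That bounds the effect of one reclassification on per-protocol membership. Protocol section 8.2.3.1 makes ITT primary, so membership of the primary analysis set does not change.

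**The case against.** The best case on the other side is that this is a conflict by default rather than by instruction. Only 7.3 says what to do after perforation, and it is unambiguous. The sentence after the side-effect list in 6.1 is permissive, Table 4 is presented as guidelines, its last row is limited to prolonged and clinically significant toxicity, and it never names perforation. A specific instruction is ordinarily read as prevailing over a general one. A perforation that qualifies as a serious adverse event must also reach the sponsor within 24 hours, which gives a chance to intervene.

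Much of that stands, and it limits the point. It does not remove it. The general rule in 6.1 is not permissive: the dose will be decreased regardless of severity. Because 6.1 repeats the special handling for two other serious events, a reader can reasonably take its exceptions as complete. The protocol does not say that 7.3 overrides 6.1, and expedited reporting is not a dosing instruction.

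Two stronger readings are not supported:

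- A reader might infer that **ILD** has the same conflict. It does not. Section 6.1 directs discontinuation once ILD is diagnosed, as 7.3 does, and considers resuming drug only if ILD is excluded. The absence of an ILD row in Table 4 is a matter of layout. The ILD incidence quoted in 7.3 therefore says nothing about the size of the perforation problem.
- A reader might infer that the **missing upper grade limit** in the Other toxicity row is itself a contradiction, because the diarrhoea and rash rows stop at Grade 4 and the keratitis row at Grade 3 or above. Different rows may have different rules, and no passage conflicts with the open-ended row on grade alone.

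**Conclusion.** The point holds for gastrointestinal perforation only. It is an internal contradiction in the Protocol: 6.1 and Table 4 leave a reduce or hold-and-restart route open by default, and 7.3 directs permanent discontinuation. It is wrong as written and should be corrected, because the disagreement concerns re-exposure after an event that the protocol says can be fatal.

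The number of patients is small and cannot be estimated from the documents, which say only that perforation is uncommon. The effect on the analysis is secondary: an ambiguous Table 6 coding that could move an affected patient in or out of the per-protocol set.

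The conclusion rests on two assumptions: that a site may consult 6.1 and Table 4 without also consulting 7.3, and that a perforation can be judged prolonged and clinically significant and then recover within the 14-day holding limit. It implies no view on which clinical instruction is right.

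**What to change.** Reconcile the section 6.1 side-effect list and general reduction rule, the Other toxicity row of Table 4, and the perforation paragraph of section 7.3. State in section 6.1 and in a Table 4 footnote which passage governs gastrointestinal perforation. The choice of clinical rule belongs to the sponsor. Once it is made, the Table 6 coding of such a patient can be judged against a single rule.

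The cost is about one sentence and one footnote, made by protocol amendment. No assessment, visit, sample size or analysis method changes.
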